## 12.0 Study Design/Procedures

### Directions:

- 1) **Describe the overall study design (e.g.: single visit, single-blind, double-blind, non-randomized, randomized, blood draw, investigational drug, device etc.).**
- 2) **Provide a description of all study-related research procedures being performed, including the length of time involved.**
- 3) **Include procedures being performed to monitor research participants for safety or minimize risks.**
- 4) **Describe the source records including medical or educational records, which will be used to collect data about subjects.**
- 5) **Include a description of any device being used to collect data (e.g., eye tracker, step counter). If the device itself is being studied, include additional information in Section 29.**

1. The study follows a randomized controlled trial with a delayed intervention control design. The immediate cooking class group will receive their intervention in week 3 of the study, and the delayed cooking class group will receive their intervention in week 13 of the study.

2. *Baseline assessment meeting:* Regardless of randomized group, all participants will attend this meeting in week 1. Participants will come to a branch of the Cleveland Public Library to sign their consent form and complete the survey portion of their baseline assessment, consisting of Percieved Stress Scale, USDA Food Security Screener, and the Food Literacy, Environment, and Waste (FLEW) assessment which will be conducted via Qualtrics on tablets provided by the researchers. Two aspects of the baseline evaluation will be conducted after the baseline meeting: a) a series of two 24-hour dietary recalls (via phone calls) lasting approximately 30 minutes each and b) participants will be asked to weigh and log their food waste for one week. During the baseline assessment meeting, participants will be asked to share their phone number and participants will be given a kitchen food scale and waste log. They will be asked to return the log on the first day of class. Additionally, participants will be told what they can expect to happen at each Nourish class and will be coached on how to sign up for GroupMe to receive out-of-class information about Nourish. The duration of the baseline assessment meeting will be

approximately 60 minutes, and will occur two weeks before the immediate cooking classes group's 8-week Nourish class sessions begin.

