*Weekly Nourish classes:* Each Nourish class will last 90 minutes, and will run for 8 consecutive weeks, with one class per week. The immediate cooking class group will receive the Nourish classes in weeks 3-10, and the delayed intervention group will commence the Nourish intervention in weeks 13-20 (after the second intervention assessment period is complete).

Nourish will be held in the teaching kitchen at Dave's Market or CornUcopia. Each class will involve brief instructional video clips, hands-on cooking and tasting experiences. Participants will work individually and as part of small groups during instructional sessions. At the end of each class, participants will receive a grocery bundle and a kitchen gadget that serves both as an incentive and implementation support to promote improved cooking frequency and confidence. Participants will be asked to post photos of what they made with their groceries to the GroupMe, and we will encourage them to engage with fellow classmates on the GroupMe to encourage social support of cooking. Participants will earn raffle tickets for each time they post to the GroupMe and attend a class. A raffle drawing for a pressure cooker will be done at the second-assessment meeting (week 12) for the immediate cooking class group and at the last Nourish class for the delayed group (week 20).

The delayed intervention group will commence the Nourish intervention after the post-intervention assessment period is complete (in weeks 13-20).

A research assistant will attend each class to observe time use and lesson objectives covered.

*Second assessment meeting:* Participants will come to a branch of the Cleveland Public Library to complete their post assessment, consisting of PSS, USDA Food Security Screener, and the FLEW, as well as their return food waste log. Additionally, participants will be encouraged to enroll in an optional focus group series to provide feedback on Nourish. The duration of the second-assessment meeting will be approximately 35 minutes, and will occur in Week 12.

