## 15.0 List of Data to be Collected

1. *Indicate what identifiers you will collect*

- Name
- Address (e.g., Zip code, other geographical designation, etc.)
- Dates related to an individual (e.g., Date of admission, birth, surgery, etc.)
- Telephone number
- Fax number
- Email address
- Social security number
- Medical record number
- Health plan beneficiary number
- Account number

- Certificate/license number
- Any vehicle or other device serial
- Device identifiers or serial numbers
- Web URL
- Internet protocol (IP) address
- Finger or voice prints (*includes audio recordings*)\*
- Photographic images (*includes video recordings or CTs or MRIs of heads*)\*
- Other: Any characteristic that would uniquely identify the individual  
 If other, please explain: [Click here to enter text.](#)
- None

\*-Please note, audio or video recordings on smart phones is not allowed. Devices must be encrypted.

2. List all other data to be collected for the research study. Attach all data collection tools on the Local Site Documents page of the SpartaIRB smart form (Other Attachments).
  1. 8 post-class surveys per participant
  2. 2 Perceived Stress Scale per participant
  3. 2 USDA Food Security Screeners per participant
  4. 2 FLEW assessments per participant and food waste tracking logs
  5. 4 24-hour dietary recalls per participant
  7. Data from 2 semi-structured focus groups

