## 17.0 Data Analysis Plan

**Directions: Describe the data analysis plan, including any statistical procedures. If applicable, provide a power analysis, and study/safety endpoints.** Descriptive statistics of Likert scale weekly class survey questions and thematic analyses of weekly survey open-ended questions and focus groups will be used to assess participant perspectives of the pilot study. Classroom observation notes will be used to determine whether the Nourish and intervention is delivered as intended. Feasibility of recruitment and retention will be based on the number of participants recruited and retained through to completion of post-intervention assessments. In addition, we will analyze the pilot data collected. A series of one-way analysis of covariance will be conducted to determine statistically significant differences at post-intervention between the intervention and delayed intervention control groups on each outcome variable, controlling for the pre-treatment assessment scores on the variable analyzed. Outcome variables consist of total volume of food waste, FLEW assessment scores, food security, perceived stress, and diet quality as assessed by the Dietary Inflammatory Index.

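### Food waste is weighed but analysed as a total volume with no rule for incomplete logs, so unequal logging between arms would bias the comparison in either direction

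*Combined protocol and SAP*

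**What the plan says.** - **Measurement (section 12.0, baseline assessment meeting).** "participants will be given a kitchen food scale and waste log", and "participants will be asked to weigh and log their food waste for one week".
- **Second assessment (section 12.0).** The log is handed in at the week 12 meeting ("as well as their return food waste log"). The number of days it should cover is not given.
- **Data list (section 15.0).** The entry is "2 FLEW assessments per participant and food waste tracking logs". It states no number of days and no minimum for a valid log.
- **Analysis (section 17.0).** The outcome is "total volume of food waste". It is analysed by one-way ANCOVA to "determine statistically significant differences at post-intervention between the intervention and delayed intervention control groups", "controlling for the pre-treatment assessment scores on the variable analyzed".
- **Related provisions.** Section 26.0 pays $125 at each assessment for completing the survey, the waste tracking and the diet recalls, without defining completion in days. Section 28.0 describes daily completeness checks for the post-class surveys during the eight-week curriculum and does not mention the waste logs.

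The return date of the baseline log also needs reconciling: "They will be asked to return the log on the first day of class". Read literally, for the delayed group that is week 13, after the week 12 assessment.

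**The concern.** A scale gives mass, and no section describes a volume measurement or a conversion, so the named variable does not match the data collected.

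The more serious issue is the word total. A sum over a self-kept diary depends on two things: how much food was wasted, and on how many days the participant made an entry. With no denominator and no rule for gaps, the two cannot be separated. A participant who logs fewer days appears to waste less.

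If logging differs between arms at the second assessment, the ANCOVA estimates a mixture of waste and diary-keeping. The one-week window is stated only for baseline, so if participants keep the second log for different lengths of time, even conscientious logs would not give comparable totals.

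**Working it through.** The documents give no effect size, standard deviation, alpha or power for food waste, so there is no figure to reproduce. The group sizes (20 and 20) come from section 5.0 and the seven-day window from the baseline instructions in section 12.0. Days logged, variability and a two-sided 0.05 level are assumptions.

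**Step 1: one participant.** If missed days resemble logged days, expected total = (days logged / 7) × true weekly total.

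- 6 of 7: 6/7 = 0.857, or 14.3% too low
- 5 of 7: 5/7 = 0.714, or 28.6% too low
- 4 of 7: 4/7 = 0.571, or 42.9% too low

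**Step 2: between arms, no true effect.** Expected difference, as a share of the true weekly mean = (days in immediate arm − days in delayed arm) / 7.

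- 5 v 6 days: −1/7 = −14.3% (relative to the control arm's observed total, 5/6 = 0.833, or 17% lower)
- 4 v 6 days: −2/7 = −28.6%
- 6 v 5 and 6 v 4 days: +14.3% and +28.6%

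**Step 3: a true 25% reduction.**

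- Equal logging of 6, 5 or 4 days: 0.25 × 6/7, 5/7 or 4/7 gives 21.4%, 17.9% or 14.3%. The ratio between arms is unchanged, but ANCOVA on the total estimates the absolute difference, and that shrinks.
- Immediate arm 6 days, delayed arm 4.5 days: 0.75 × 6/7 − 4.5/7 = 0. The effect disappears.

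**Step 4: simulation of the planned ANCOVA.** 20 per arm and 4,000 runs per scenario. Assumptions: between-household coefficient of variation 0.4 or 0.8, exponential day-to-day variation, 6 of 7 days logged on average at baseline, days missed at random. Ranges cover the two coefficients of variation, with no true effect.

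| Mean days logged, immediate v delayed | Raw total: difference | Raw total: false positives | Per logged day: false positives |
|---|---|---|---|
| 6 v 6 | −0.4% to +0.3% | 4–5% | 4–5% |
| 5 v 6 | about −14% | 13–16% | 4% |
| 4 v 6 | −28% to −29% | 38–54% | 5% |
| 6 v 5 | +13% to +14% | 12–16% | 4–5% |
| 6 v 4 | +27% to +28% | 39–52% | 5% |

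The difference per logged day stays within 0.5% of zero in every row. With a true 25% reduction, the per-logged-day analysis returns −24% to −25% whether logging is equal or not. The raw total returns about −21%, −17% to −18%, or −14% at equal logging of 6, 5 or 4 days, and about 0 at 6 v 4.5.

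**Step 5: why a zero entry is needed.** Take a log with five entries and two blanks. If the blanks are missed days, the total is 28.6% too low. If they are truly waste-free days, the total is right, but dividing by 5 instead of 7 makes the daily mean 7/5 = 1.4 times the truth, or 40% too high. Only the log itself can separate the two cases.

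**The case against.** Two stronger readings are tempting, and the documents support neither.

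- **That the plan defines unlogged days as zero.** Section 17.0 gives no summing rule and no treatment of gaps. Zero-counting is what a plain sum does in the absence of a rule. It is an inference from silence.
- **That poor logging will look like an intervention benefit.** The test is between arms, so this happens only if the immediate arm logs less at the second assessment. Eight weeks of tasks might tire that arm, but eight weeks of classes and group contact might equally make it the better logger. The documents do not settle this.

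Other points in the plan's favour carry weight. In ordinary use volume can mean amount, and an analyst who knew about the scales would probably use weight, so that word alone is mostly editorial. The log form is not in the text and may already have daily rows or a zero box. The $125 payment may limit missing days, and no difference by arm is stated. This is a feasibility pilot, the ANCOVAs are an addition to its main aims, and no decision rule rests on this outcome. Finally, a mean per logged day is not automatically better: it assumes days are missed at random, and without recorded zeros it can overstate waste.

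These points limit how serious the problem is. They do not supply the missing definition: neither a payment for completion nor a well-designed form tells the analyst what to do with a five-day log.

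**Conclusion.** The point holds as a gap in the outcome definition that is cheap to close. The named variable does not match the measurement, the second logging window is not stated, and there is no rule for incomplete logs. On a plain total, each missed day of seven costs about 14% of that participant's recorded waste. An average gap of one day between arms moves the comparison by about 14% of the true mean, in a direction set by which arm logs less, and raises the false-positive rate from about 5% to between 12% and 16%. Equal under-logging creates no spurious difference but shrinks a real one.

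These sizes rest on assumed completion rates and variability and on missed days resembling logged ones. The documents contain no evidence on how complete the logs will be in either arm. Because this is one of several outcomes in a pilot, the point is a recommended improvement and does not threaten the trial's main aims.

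**What to change.** In section 17.0, define the outcome as mean weight of food waste in grams per logged day. State the same logging window for baseline and the second assessment. Require an entry every day, with an explicit option for a day without waste if the form does not already have one. Pre-specify the minimum number of valid days; 4 of 7 would be one choice, but the documents give no basis for a particular figure. Report days logged by arm and assessment as a result on the feasibility of the evaluation methods (Aim 2 in section 2.0), which section 17.0 at present measures only through recruitment and retention. Reconcile the return date of the baseline log for the delayed group.

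The cost is a few sentences and perhaps a tick-box. A few very incomplete logs become missing, and the daily mean still assumes that days are missed at random. The zero entry must be in place before logs are issued, because waste-free days that were left blank cannot be recovered later.

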## 18.0 Confidentiality of Data

1. To maintain the confidentiality of the data:

I will use a unique study identifier to code individuals' identifiable data and will store the master list separate from the study data.

I will use a unique study identifier to code individuals' data, but it will never be linked to a master list.

Other- please explain: [Click here to enter text.](#)

Provide a plan to maintain or destroy identifiers once analysis of identifiable information is complete. Identifiers will be securely stored in box and maintained throughout the delayed control intervention. One year after analysis of identifiable information is complete, identifiers will be deleted.

I attest that any recordings (audio or video) saved to a portable device will be deleted by formatting the device's storage memory.

How are you storing your electronic data?

CWRU Redcap

CWRU Secure Research Environment (SRE)

CWRU Box

OnCore

CWRU Secure Network Drive, Which one?: [Click here to enter text.](#)

Zoom Cloud

Portable device (must be encrypted, not just password protected)

Other - List storage method and provide justification: Click here to enter text.

*Please note: if you're storing or entering your electronic data in any system other than an approved system listed above, please contact the CWRU IRB ([[contact]](mailto:[contact])).*

Excluding the above, are you using any cloud-based software or websites (i.e data has to go over the internet to be processed) to analyze data?

If so, please list below. E.g., transcription services, qualitative analysis services, etc. You may be asked to provide more information.

Yes Please describe: Transcription service for online focus group sessions. Online focus group discussions, hosted by CWRU Zoom, will be audio recorded and recordings will be transcribed using NVivo Transcriptions. Audiorecordings will be deleted after transcription verification process is complete. Transcriptions will be uploaded into Nvivo 14. This software supports qualitative and mixed methods research that, relevant to Nourish, allows the research team to organize and analyze focus group discussion content via search, query, and visualization tools.

No

2.  I acknowledge that paper research data and documents will be stored in a double-locked secure environment in the following **location**: *Documents will be double-locked and stored within the principal investigators office suite at [name].*

We will not have paper research documents.

3. Will data be shared with to institutions/persons outside of CWRU?

Yes

- With whom will data be shared? Click here to enter text.
- List the exact data elements that will be shared: Click here to enter text.
- Describe how data will be sent: Click here to enter text.

No

N/A

*If sharing data, please complete a request to ensure the proper contracts/agreements are in place: <https://case.edu/research/faculty-staff/technology-transfer/material-transfer-data-use-agreements>*

## 19.0 HIPAA Authorization

Does this study collect, access, use, or distribute any Protected Health Information (PHI)?  
*Protected Health Information (PHI) is (1) any individually identifiable health information transmitted or maintained in a medical record, paper or electronic, or (2) designated data set that was created, disclosed, or used in the course of providing a health care service such as diagnosis, payment or treatment.*

Yes       No

If yes, indicate how HIPAA authorization will be obtained (check all that apply):

- HIPAA authorization is in the consent form
- I am receiving a Limited Data Set under a Data Use Agreement (DUA)
- Requesting a full or partial waiver of HIPAA for prescreening
  - I will complete the Request for Waiver of HIPAA Authorization form. *See SpartaIRB Library*
- Requesting a full or partial waiver of HIPAA
  - I will complete the Request for Waiver of HIPAA Authorization form. *See SpartaIRB Library*

## 20.0 FERPA Authorization

Does this study collect, access, use, or distribute any personally identifiable information from student records or personal education information from an education program (defined as: any program principally engaged in the provision of education, including, but not limited to, early childhood education, elementary and secondary education, postsecondary education, special education, job training, career and technical education, and adult education)? This includes, but is not limited to, classroom assignments and course evaluations.

Yes       No

If yes, how do you plan to get written authorization from the student (or parent if the student is a minor)?

- I will incorporate FERPA language\* into the consent and obtain written and dated signature or authorized electronic signature using REDCap
- I will incorporate FERPA language\* into a separate form and obtain written and dated signature or authorized electronic signature using REDCap

## 20.0 Risks to Research Participants

1. List the reasonably foreseeable risks such as breach of confidentiality, discomforts, hazards, or inconveniences to the research participants related to their participation in the research. Include a description of the probability, magnitude, duration, and reversibility of the risks. Include the physical psychological, social, legal, and economic risks.  
DO NOT REPLY WITH “NO RISKS” For example, loss of privacy, boredom, emotional distress, etc.

Participation in the Nourish Pilot may result in participant inconveniences due to the requirement to travel to the meeting location for baseline/first and second assessments and for each in-person class. There is a low probability that the social aspect of the class setting may result in social risks, including embarrassment and frustration. The baseline/first and second assessments may cause some participant emotional distress due to topics of mindless eating and food waste. There is a low probability that participation in the codesign focus groups may result in discomforts and social risks, including

\* FERPA language: 1. Specify the educational records that may be both accessed and used in the research. 2. State the purpose of the access and use of records. 3. Identify to whom the records disclosure may be made.

embarrassment, frustration, or anger. It is anticipated that these risks are reversible and will, thus, not extend beyond the duration of each step in the study design, including not extending beyond class time, the duration of the assessments, and the duration of the focus groups. The magnitude of these risks is low due to minimal probability and severity.

2. If applicable, indicate which experimental procedures may have risks to the research participants that are currently unforeseeable. [Click here to enter text.](#)  
 N/A
3. If applicable, describe the risks to others who are not research participants. [Click here to enter text.](#)  
 N/A
4. Describe the availability of medical or psychological resources that research participants might need. [Click here to enter text.](#)  
 N/A

## 21.0 Provisions to Protect the Privacy Interests of Research Participants

**Directions: Indicate the measures that will be taken to protect research participants' privacy interests. Select all that apply:**

- In person interactions will be conducted in a private space where conversations would not be overheard by others -- this could be at a specific location determined by the research team or at a location that the participant chooses.
- For online/remote data collection, participants will be advised to choose a location that would be private.
- Researchers will only contact participants if permission has been given to do so.
- Other: In person interactions, in the form of class time, will be conducted within the teaching kitchen, which will only be accessible to enrolled participants of the Nourish Pilot Study. For the online focus groups, participants will be requested to choose a private location and keep discussions confidential.

## 22.0 Potential Benefit to Research Participants

- There is potential benefit to research participants.

Describe the potential benefits that individual research participants may experience from taking part in the research. Include the probability, magnitude, and duration of the potential benefits. *Do not list compensation.* During each of the 8 classes, Nourish participants will receive food during class and groceries and cooking supplies to take home that serve as implementation supports for continued meal preparation and cooking behaviors at home. We also expect that participants will also gain knowledge regarding improv cooking, food safety, and nutrition, and benefit from improved culinary nutrition skills and food literacy.

- There is no direct benefit to research participants.

If no direct benefit, state the potential benefit to society or others. *Do not list compensation.* Click here to enter text.

